## 2.7. COMPLAINT FORM

Before the start of the interventions, each participant will be given a complaint form to submit their possible complaints and record the problems they may have encountered and/or their observations regarding the provided interventions, the overall design and organization of the research, the scientific group or anything else worth mentioning.

# 2.8. PROCEDURE

Initially, the prospective participants who will come from the structures mentioned in the section "Conducting research - Declaration of consent" will send through their electronic mail or by hand their medical diagnosis. The latter, combined with the exclusion criteria set, will be the way to sort the appropriate population. Participants will complete their consent form and demographic information. A full musculoskeletal assessment by an experienced physical therapist trained in the identification of myofascial pain trigger points (MTrPs) will be required at the start of the A-S group protocol. The determination of each MTrP will be achieved by palpation of the muscles under examination - upper trapezius and levator scapulae - based on the criteria of Travell and Simons (1992). The points will be marked with an indelible ink and recorded on a body chart. The skin will be cleaned with alcohol before the start of the intervention. The ATM technique requires no preparation.

During the intervention period (five weeks) the exact protocol will be followed, as analyzed in the corresponding subsections "Group A-ATM (FM)" and "Group BA-S". Acupuncture sessions will take place in the Pain Clinic of the Aretaeio hospital and will be carried out at ambient temperature (25°C) as the reduced temperature causes vasoconstriction making it difficult to apply acupuncture. The treatment area

will be quiet, sunny and clean. The two interventions will take place in the morning and afternoon, from 8.30 am to 6.30 pm.

Measurements will be carried out at the time points before the start of the intervention, after completion and at the follow-up at four months. In detail, PPT, ROM of flexion-extension, rotation and side flexion and neck position sense, respiratory function and flexor muscle strength will be recorded while patients will complete all seven questionnaires. From the total sample number, the patients participating in the follow-up will be calculated and therefore the cumulative dropout rate will be derived, which will be allocated to the two groups. Those who do not successfully complete treatment will be asked about the reasons that contributed to this. Finally, adverse effects from the application and/or ATM will be recorded.

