# 2.5. MATERIAL AND METHOD

## 2.5.1. SAMPLE

## 2.5.1.1. SAMPLE CHARACTERISTICS

During the initial calculation of the sample number, the number of the participants was determined, with purpose, the method of Analysis of Variance (ANOVA) in two groups of equal population, to identify a standardized effect size equal to 0.25 with a power of 80% and a level of statistical significance of 5%. The standardized effect size is defined as follows: Let the measurement tool X and groups A, B and  $\mu$ A,  $\mu$ B

be the mean values of X in groups A and B. SD is the Standard Deviation of X in the whole population. The effect size is given by the formula  $(|\mu A-\mu B|)/SD$ . The calculation was performed with the program G\*power version 3.1.9.7\* and the necessary sample size was calculated at 126 subjects. According to the relevant literature, similar standardized sample sizes have been used in two studies dealing with chronic neck pain (Lundblad *et al.*, 1999; Malmgren-Olsson *et al.*, 2009). Moreover, a dropout rate of 20% was expected, so a final number of around 152 patients is realistic for this study.

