2013). The first assessor will administer the consent form, the demographic characteristics form, the questionnaires and recorded the primary outcome measures, as well as the secondary outcome measure prior to the start of the study. The second assessor will administer the compliance and complaint form to the participants and will record the primary outcome measure and the secondary outcome measures after the completion of the interventions. Data analysis will be performed by an independent biostatistician, an associate of the Musculoskeletal Physiotherapy Research Laboratory of the University of West Attica (UNIWA), who will not know the group in which each participant will have been allocated.

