#### 2.5.3. OUTCOME MEASURES

Primary outcome measures will be the sensitivity of pain and secondary outcome measures will be the ROM of flexion, flexion-extension and lateral flexion of the cervical spine, the endurance of the deep flexor muscles of the cervical spine, the respiratory function, the intensity as well as the sensory and affective dimensions of the pain, the functional capacity of the neck, the anxiety and depression, the fear of movement, the perception of fear and the attempt to avoid pain in relation to physical and work activities, the degree of destructive views about pain, the quality of life and patients' perceived change in their health conditions. Furthermore, the compliance rate will be recorded.

The measuring tools were selected based on their validity, reliability, ease of application and clinical economy. The outcome measures were assessed before the start as well as at the completion of the therapeutic interventions at five weeks, for both groups.

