# 2.9. STATISTICAL ANALYSIS

Quantitative variables will be expressed as mean and standard deviation (SD). Qualitative variables will be expressed as absolute (N) and relative (%) frequencies. Pearson's  $\chi^2$  test and Fisher's exact test (where it is necessary) will be used to compare proportions, as well as McNemar test will be used to compare the percentages of kinesiophobia between measurements. Student's t-test or nonparametric criterion Mann-Whitney will be used for the comparison of the quantitative variables between the two groups. The change in the used scales and other indicators of the participants over time will be tested using linear mixed models from which dependence coefficients ( $\beta$ ) and their Standard Errors (SE) will be obtained. The group, the measurement (endline vs baseline) and their interaction term (to be tested in which extent the change is different between measurements in the two groups), will be introduced as independent variables. In the cases, where the interaction term will be found significant, sex, age, BMI and the symptoms duration will be introduced in the model (the chosen confounding factors are the most significant), in order to be tested if the interaction remain significant. Moreover, in the case that measurements at some outcome measures will be found to differ significantly at the initial measurement between the two groups, a result not due to systematic error but found to be due to random sampling. In these cases, their initial values will be entered into the mixed linear models as an independent variable to ensure that the findings from the models are not due to the initial differences between the groups. In cases that will be found significant differences between baseline measurements, between the two groups, the initial measurements will be introduced in linear mixed models as independent variable, in order to be ensured that the findings from these models are not due to initial differences between the groups. All reported p values will be two-tailed and statistical significance will be set at p < 0.05. Analyses will be conducted using the IBM SPSS Statistics 26.0.

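### Endline is scheduled only at or after completion of treatment, and the plan gives no measurement, analysis set or missing-data assumption for patients who stop early

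*Combined protocol and SAP*

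**What the plan says.** - **Timing of endline.** Section 2.5.1.2 says that the second assessor "will record the primary outcome measure and the secondary outcome measures after the completion of the interventions". Section 2.5.3 says that outcomes are taken "before the start as well as at the completion of the therapeutic interventions at five weeks, for both groups". Sections 2.8 and 2.10 also place the post-treatment measurement after completion, and 2.10 adds five weeks. The compliance form in Section 2.6 is filled in once the ten sessions are over.
- **Patients who stop.** Section 2.8 derives a dropout rate from attendance at follow-up and then states: "Those who do not successfully complete treatment will be asked about the reasons that contributed to this". It describes no other data collection for them.
- **Expected loss.** Section 2.5.1.1 states that "a dropout rate of 20% was expected" and raises the target from 126 to about 152.
- **Analysis.** Section 2.9 plans linear mixed models with group, time and their interaction, t-tests or Mann-Whitney tests between groups, and McNemar tests for kinesiophobia. It names no analysis set, missing-data assumption or sensitivity analysis for missing values.

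**The concern.** Both main hypotheses concern pressure pain threshold: its change under ATM, and the difference in change between ATM and A-S. Both need endline values. A site that follows the text has no instruction to recall a patient who stops in, say, week two. If such patients are not measured, those who stop because they are not improving, or because they dislike needling or the class format, are missing for reasons linked to treatment and outcome.

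The reasons need not be the same in the two arms. ATM is taught in groups at a community centre and A-S is given individually at the hospital (Section 2.5.1.3). All assessments take place at the hospital, so an ATM patient who has stopped must travel to a different site to be measured. This makes unequal loss plausible but does not show that it will occur. A five-week value not taken at the time cannot be recovered later.

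**Working it through.** **Inputs from the documents.** Two-sided 5% level ("All reported p values will be two-tailed and statistical significance will be set at p < 0.05", Section 2.9). From Section 2.5.1.1: 80% power, "standardized effect size equal to 0.25", 126 evaluable, about 152 enrolled, 20% dropout. From Section 2.5.1.2: 76 per arm. The effect is a mean difference divided by SD, where "SD is the Standard Deviation of X in the whole population". No value of that SD is given, so results stay in SD units.

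**Assumed, not in the documents.** The gap d by which non-completers improve less than completers (0.25, 0.50 or 0.75 SD), and the split of loss between arms.

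**1. The plan's sample size.** With the normal approximation, n per arm = 2(1.960 + 0.842)²/δ².
- δ = 0.5: 2 × 7.85/0.25 = 62.8, so 63 per arm and 126 in total. ANOVA with Cohen's f = 0.25, which for two equal groups is δ = 0.5, gives 128. The plan's 126 is reproduced.
- δ = 0.25, as the section defines the effect: 2 × 7.85/0.0625 = 251.2, so 252 per arm and 504 in total (506 by ANOVA).

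The mismatch is a separate matter. Here it means only that the design effect is 0.25 or 0.5 SD, depending on the reading.

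**2. Patients with an endline value.** 126 × 1.2 = 151.2, which gives the stated 152 in two equal arms. Expected without endline: 0.20 × 152 = 30.4. Expected with endline: 0.80 × 152 = 121.6, or about 122. That is below 126 because the allowance was multiplied on; 126/0.8 = 157.5 would give 158. Power by ANOVA, assuming the same effect:

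| Patients with endline | f = 0.25 | difference 0.25 SD |
|---|---|---|
| 122 | 78% | 28% |
| 152 | 86% | 33% |

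**3. Bias of a completer comparison.** If a fraction p has no endline and these patients improve by d less, the whole-arm mean is the completer mean minus p × d. Completers therefore overstate the change by p × d, and the between-arm bias is pA·dA − pB·dB.
- ATM before/after, p = 0.20: 0.20 × 0.25 = 0.05, 0.20 × 0.50 = 0.10, 0.20 × 0.75 = 0.15 SD.
- Between arms, equal loss and equal gap: 0.20d − 0.20d = 0.
- Between arms, 30% versus 10% loss (20% overall) and the same gap: 0.20d = 0.05 to 0.15 SD.
- Between arms, 20% loss in each but a gap only in ATM: also 0.05 to 0.15 SD.

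**4. What the mixed model changes.** It keeps patients with a baseline value only. Simulation under assumptions: 76 per arm, no true effect, baseline-endline correlation 0.6, 30% loss in ATM and 10% in A-S, 4,000 repetitions. Completers' change is compared with the maximum-likelihood estimate that uses everyone's baseline.

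| Loss depends on | Between arms: completers | Between arms: likelihood | ATM before/after: completers | ATM before/after: likelihood |
|---|---|---|---|---|
| nothing | 0.00 | 0.00 | 0.00 | 0.00 |
| baseline | −0.08 | 0.00 | −0.14 | 0.00 |
| the patient's own change | 0.19 | 0.16 | 0.32 | 0.27 |

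In the last row about 84% of the bias remains (0.16/0.19 and 0.27/0.32). The gap implied there is 0.32/0.30, or about 1.07 SD, which is wider than the range in step 3. The simulation therefore shows what share the model fails to remove, not the size to expect here.

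**5. The other tests.** An endline t-test or Mann-Whitney test, and McNemar's paired test, can use only patients with an endline value.

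**The case against.** The strongest reply is that the plan is silent rather than restrictive. Nothing bars measuring a patient who has stopped, and nothing confines the analysis to completers. Section 2.5.3 mentions five weeks and both groups, and Section 2.8 gives the intervention period as five weeks, so a calendar reading is open. Section 2.8 also ties dropout to attendance at follow-up, not to stopping treatment. All of this stands. A reader might infer that patients who stop certainly get no endline, or that both questions are answered in completers by design; the documents support neither. They do leave a site without an instruction, because in Section 2.5.3 the five weeks qualifies completion.

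The mixed model is also a fair defence. It is valid if data are missing at random, and step 4 shows no bias when loss depends on baseline. It fails when loss depends on the unseen outcome, and with one post-treatment measurement in the core design there is no interim value to inform the missing one.

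Three further inferences should be resisted:
- That A-S sessions can be rebooked while a missed ATM lesson is lost. Both arms have ten sessions at two a week for five weeks, and nothing is said about rebooking or make-up sessions.
- That 20% is the rate of stopping treatment. It is a dropout allowance for the sample size, and some of those patients would be lost under any visit rule.
- That the comparison between arms must be biased. Equal loss for the same reasons gives zero.

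**Conclusion.** The concern holds as an omission that should be corrected. Endline is defined only through completion, the plan provides no five-week measurement for patients who stop, and it names no analysis set or missing-data assumption. Results may therefore rest largely on completers.

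Under the assumed gaps, the ATM before/after bias in a completer comparison is 0.05 to 0.15 SD, and the between-arm bias is 0 to 0.15 SD. Against the design effect, 0.15 SD is 60% if that effect is 0.25 SD (0.15/0.25) and 30% if it is 0.5 SD (0.15/0.5). The planned mixed model would leave none of this if data are missing at random, and most of it in the scenario tested where loss follows the patient's own change. The direction assumes that non-completers do worse; if they do better, the sign reverses. The before/after question is the more exposed of the two, because equal loss in both arms does not protect it.

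**What to change.** - **Sections 2.5.1.2, 2.5.3 and 2.8.** Define endline as a fixed five-week visit with a short window, counted from randomisation or from the planned start of treatment so that it also covers patients who never start. State that every randomised patient is invited, however many sessions they attended.
- **Patients who decline the visit.** Collect the questionnaires remotely and accept that pressure pain threshold will be missing, since it needs the algometer.
- **Section 2.9.** Analyse all patients by allocated arm. State the missing-at-random assumption behind the mixed model. Add a missing-not-at-random sensitivity analysis, for example one that shifts the unseen endline values by a range of amounts, separately by arm.
- **Reporting.** Give sessions attended separately from dropout, with dropout meaning no endline value. Section 2.6 describes home exercise only, so a session count should be added.

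The visit, the assessor and the instruments already exist. The cost is protocol wording, a few extra calls and invitations, and possibly slightly smaller estimated effects because patients who stopped are included. Each recovered endline also restores power, up to the figures for 152 patients in step 2.

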## 2.5.1.2. METHOD OF RANDOMIZATION AND BLINDING

The sample will include 152 patients of both sexes and age range 19-70 years. Participants will be collected using the simple random sampling method and these meeting the inclusion and exclusion criteria will be recruited and will form the study sample. The participants will be allocated using the method of simple randomization with an allocation ratio of 1:1, i.e. in two equal groups of 76 people, each.

The randomization of patients to the A ATM group and the B A-S group will be performed with the help of a random number generator created in Stata software with the help of the "randomizer" package. The "randomizer" package through the principles of binomial distribution, randomly assigns to each participant their participation in either the intervention group or the active control group. In this way each participant will be placed in one of two groups at the start of the study and will remain in the same group for the duration of the study. The ratio of subjects between the two groups will be maintained at 1:1 throughout the study.

This study is a single blind clinical trial. The intervention will be perceived by the principal researcher, who will apply the treatment protocol in the intervention group (A ATM), the physiotherapist, who will apply the treatment protocol in the active control group (B A-S) and the participants. It is not feasible for both participants and therapists to be blinded, due to the nature of each intervention. All evaluations of the effectiveness of the treatment interventions will be carried out by two independent assessors who, although belonging to the research team of the study, do not know the type of intervention that each patient will receive, as well as the allocation of patients to the different treatment intervention groups (Kang, 2013, Opara *et al.*,

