- Bladder 10 (BL 10) which is located on the horizontal line, passing between the spinous processes of the first (A1) and the second (A2) cervical vertebra and the oblique line, passing through the outer limit of the upper trapezius muscle, 1.3 Cun bilaterally of the vertical axis of the body, passing through the spinous processes of A1-A2 (Wilke *et al.*, 2014; Sun *et al.*, 2019).
- Governing Vessel 14 (GV 14) in the depression, inferior to the spinous process of the seventh cervical vertebra (A7) (Karavis, 2011; Wilke *et al.*, 2014).

General acupoints will include:

- Triple Energizer 5 (TE 5) which is located 3 cm above the joint line of the wrist, at the dorsal surface of the forearm between the radius and ulna (Wilke *et al.*,2014; Calamita *et al.*, 2018)
- Large Intestine 4 (LI 4) in the hollow of the radial side of the hand, approximately at the midpoint of the 2nd metacarpal.

After the needle will be removed, firm compression will be applied to the injection sites for 40 seconds to prevent any microbleeding (Campa - Moran *et al.*, 2015). The protocol acupoints are listed in Table 4.

Local	Regional	General
SI 14 (MTrP in the levator	Huato Jiaji C5	TE 5
scapula muscle)	BL 10	LI 4
GB 21 (MTrP in the upper	GV 14	
trapezius muscle)		
GB 20		
BL 43		

Potential events, except for dermatitis, will be managed in accordance with the "Management of Adverse Reactions to Acupuncture and Dry Needling" section of the Guide to Safe Acupuncture and Use of dry needling of the World Confederation of Physical Therapy (WCPT) and the special subgroup dealing with acupuncture (International Acupuncture Association of Physical Therapists – IAAPT). In the event of dermatitis after the application of acupuncture, a wet towel or cloth can be applied to the affected area, followed by a cream or ointment containing calcineurin inhibitors or a corticosteroid cream, gel or ointment. The affected skin can be subjected to phototherapy, i.e., controlled amounts of natural or artificial light (Dermatitis, 2020). If symptoms persist, the patient should be referred to their treating physician. It is pointed out that the side effects result from improper sterilization and use of the needles (Sfara, 2013). White (2004) estimated the risk of a serious adverse event to be 0.05/10.000 treatments and 0.55/10.000 patients.

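### Harms recording is limited to effects attributed to treatment, with no common questioning across two differently observed arms and no harms summary, so non-serious harms may be under-recorded, possibly unequally

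*Combined protocol and SAP*

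**What the plan says.** **Recording rule.** Section 2.8 ends with one sentence on harms: "Finally, adverse effects from the application and/or ATM will be recorded". It does not say what counts as an adverse effect, who asks, when, how severity is graded or who decides on cause. The same section says that patients who do not complete treatment will be asked why.

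**Complaint form.** Section 2.7 says "Before the start of the interventions, each participant will be given a complaint form to submit their possible complaints" and lets them "record the problems they may have encountered and/or their observations regarding the provided interventions". Section 2.5.1.2 says "The second assessor will administer the compliance and complaint form to the participants"; the same sentence has this assessor record the primary outcome and "the secondary outcome measures after the completion of the interventions".

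**Acupuncture events.** The Group B A-S section (2.5.2.2 in the contents, printed as 6.5.2.2) refers to a safety guide for managing events, adds steps for dermatitis, and remarks: "It is pointed out that the side effects result from improper sterilization and use of the needles". It cites serious-event risks of 0.05 per 10,000 treatments and 0.55 per 10,000 patients. The ATM section has no counterpart.

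**Analysis and reporting.** Harms do not appear in the outcome list (2.5.3), the statistical analysis (2.9) or the results plan (2.10).

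**The concern.** A rule that records effects from a treatment builds attribution into the record. An event that nobody links to the treatment, such as a flare after home exercise, need not be written down, and the data would not show that it was left out.

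The second problem is comparability. Patients in the two arms meet staff in different settings and formats. Without the same question at the same times, a difference in harm counts could reflect how patients were observed and not what the treatments did. With no planned tabulation, even the events that are recorded may never be set out by arm.

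The efficacy conclusions are not at stake. What is at stake is any statement about the tolerability of ATM, alone or against A-S.

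**Working it through.** The plan gives no figure for this point, so the main check sets the sections side by side.

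**1. What the application could mean.** The document uses the word application for ATM and for A-S as a whole (hypotheses in 2.3), and for acupuncture alone (the dermatitis text in the Group B section). In the 2.8 sentence it stands beside ATM without a noun. If it means A-S, home stretching is covered. If it means acupuncture, the daily home stretching in the Group B section is not. The text does not settle this.

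**2. Opportunity to notice events.**
- A-S: ten individual sessions of 40 minutes (Group B section) at a hospital pain clinic (2.5.1.3), plus daily home stretching.
- ATM: ten sessions of 50 minutes in groups of 6-8 (Group A section) at a municipal centre (2.5.1.3), led by the principal researcher (2.5.1.2), plus home exercises on the remaining days.
- Session numbers match, but setting, privacy and staff do not. No common question is specified.

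**3. Complaint form.** Section 2.7 hands it out before treatment. Section 2.5.1.2 gives its administration to the assessor who measures after treatment. Neither says when or how it is returned during treatment or by someone who leaves. That assessor is meant to be blind and records the post-treatment primary outcome, yet handles a form that invites comment on the treatments received.

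**4. Cause of needle side effects.** The Group B remark attributes side effects in general to sterilization and needle use. Table 2 excludes metal allergy and previous adverse reaction to acupuncture (items 21 and 22), which are patient characteristics. The two can be squared if the remark covers only the risk left after those exclusions, but the remark does not say so.

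**5. Which harms this trial could see.** Inputs: 76 patients per arm (2.5.1.2), 10 acupuncture sessions each, and the cited risks.
- Treatments: 76 × 10 = 760.
- Expected serious events, per-treatment rate: 760 × 0.05/10,000 = 0.0038.
- Expected serious events, per-patient rate: 76 × 0.55/10,000 = 0.0042.
- Chance of at least one: 1 − (1 − 0.000055)^76 = 0.42%.
- One-sided 95% upper bound if none occurs in 76: 1 − 0.05^(1/76) = 3.9%.

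On the plan's own figures, the observable acupuncture harms are almost entirely non-serious. Those depend most on how patients are asked.

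**6. Illustration, with assumed rates.** The documents give neither a non-serious event rate nor a capture rate. Expected patients with a recorded event = 76 × true rate × capture:

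| Assumed true rate | Full capture | Half capture |
|---|---|---|
| 10% | 7.6 | 3.8 |
| 20% | 15.2 | 7.6 |
| 30% | 22.8 | 11.4 |

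With equal true rates of 20%, full capture in one arm and half in the other would give 15.2/76 = 20% against 7.6/76 = 10%. This shows the mechanism and is not an estimate.

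**The case against.** The strongest defence is that the 2.8 sentence is loose, possibly translated wording that simply means adverse effects in either arm. Other channels exist. The complaint form is open-ended and has no cause condition, and non-completers are asked their reasons. GPE asks about worsening, and NDI and SFMPQ are repeated at the end, so worsening that lasts would show in both arms. Patients are seen twice a week. The informed consent form listed in the contents was not in the text available and could hold reporting instructions.

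Much of this stands as a limit on the claim. It does not close the gap: none of these channels collects dated, graded events by the same method in both arms, and the scales miss events that resolve before the end.

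A reader might also infer stronger points that the documents do not support:
- **Therapists decide what counts.** No causality judgement and no judge is described, and 2.8 does not say who records.
- **The complaint-form sections contradict each other.** They can be read together as handed out early and gone through or collected late. The reference to completion attaches grammatically to the outcome recording. This is an ambiguity.
- **The remark on needle use deters reporting.** It is a cited literature remark in a paragraph on managing events. A motive to conceal is speculation.
- **Home days or dropout measure the loss.** Home ATM could fill up to 25 of 35 days (71%), but that counts days, not events, and is an upper bound. Dropout of 20% of 152 is about 30, or 152 − 126 = 26 from the plan's own totals, but nothing says that all of them leave during treatment or never return a form.
- **Harms will be under-recorded.** The documents support may, not will.

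**Conclusion.** The concern holds in a limited form. The rule in 2.8 restricts recording to attributed effects, leaves its scope unclear for home stretching, and sets no common questioning in two arms that differ in setting and contact. Sections 2.9 and 2.10 plan no harms summary. Non-serious harms may be under-recorded, possibly unequally between arms, and the counts as planned would not be safely comparable.

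The size and direction of any imbalance cannot be computed. The conclusion rests on the text available, which excludes the consent form, and on the cited serious-event rates applying to this sample. The change should be made before recruitment or as early as possible, because events not asked about at the time cannot be reliably recovered later.

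**What to change.** - **Section 2.8.** Replace the sentence with a rule that any untoward event or worsening of symptoms is recorded whatever its presumed cause, including during home ATM exercises and home stretching, with date, severity and outcome. Put the same open question in both arms at every session already scheduled, at withdrawal and at the end assessment. Keep relatedness as a separate field. At the end assessment, take the answer in a way that does not reveal treatment to the blinded assessor.
- **Sections 2.9 and 2.10.** Add a table by arm of patients with at least one event and of numbers of events.
- **Sections 2.5.1.2 and 2.7.** State one timing for the complaint form: held from the start and returnable at any time, including at withdrawal. The route must work at both sites, for example a sealed envelope, and keep the contents from the outcome assessor.
- **Group B A-S section.** Reconcile the general remark on the cause of side effects with exclusion items 21 and 22, so that it is not read as limiting what is recorded.

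The cost is protocol wording, slightly more paperwork at existing visits, and a longer list of minor, unrelated events. One limit remains: the therapists at those visits are unblinded, so fixed wording reduces observer influence but does not remove it.
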